4. SELECTION AND ENROLLMENT OF PARTICIPANTS

4.1. INCLUSION CRITERIA

- (1) Age: 50 years or older;
- (2) MCI group will be defined based on:

- (i) Subjective memory concern;
- (ii) Abnormal memory function documented using the Logical Memory subscale (Delayed Paragraph Recall, Paragraph A only) from the Wechsler Memory Scale-Revised (the maximum score is 25): [<11 for 16 or more years of education; <9 for 8-15 years of education; <6 for <7 years of education];
- (iii) Montreal Cognitive Assessment (MoCA) < 26;
- (iv) Clinical Dementia Rating scale /Memory box score=0.5;
- (v) General functional performance sufficiently preserved (Functional Assessment Questionnaire ≤ 5).

(3) *Early AD dementia* group will be defined based on:

- (i) Subjective memory concern;
- (ii) Abnormal memory function documented using the Logical Memory subscale (Delayed Paragraph Recall, Paragraph A only) from the Wechsler Memory Scale-Revised (the maximum score is 25): [<11 for 16 or more years of education; <9 for 8-15 years of education; <6 for <7 years of education];
- (iii) Montreal Cognitive Assessment (MoCA) <26;
- (iv) Clinical Dementia Rating scale/Memory box score 1 or 2;
- (v) Early AD dementia defined as Functional Assessment Staging Test (FAST) of 4 or 5;

In instances where the diagnosis of early AD is not clear, a review of the subject's cognitive and non-cognitive data will be performed by the study physicians or neuropsychologists and a diagnosis of the degree of cognitive impairment will be based on the clinical judgment of the study physicians or neuropsychologists.

4.2. EXCLUSION CRITERIA

- (1) Intolerance to Montelukast;
- (2) Current diagnosis of bronchial asthma or exercise-induced bronchospasm **and** currently on Montelukast or other leukotriene receptor antagonists (Zafirlukast, Pranlukast);
- (3) Liver disease (elevated liver enzymes ($>2x$ normal): ALT, AST, alkaline phosphatase, total bilirubin);
- (4) Renal disease (Creatinine >2.0 mg/dl), platelets<50,000/ μ l, or INR>1.9;
- (5) Diagnosis of any neurological or psychiatric disorders that affects cognition such as uncontrolled depression, schizophrenia, Parkinson's disease or use of anti-Parkinsonian therapies (unless used for essential tremor), multiple sclerosis, or other active medical condition that in the judgment of the study physicians would affect the safety of the subject or scientific integrity of the study;
- (6) Other contributing factors to cognitive impairment such as uncontrolled hypothyroidism (TSH >10 mU/l) or untreated low vitamin B12 (<250 ng/mL);
- (7) Uncontrolled congestive heart failure reflected by poor exercise tolerance and shortness of breath at rest or with some exertion;
- (8) Actively undergoing chemotherapy or radiation therapy for cancer treatment;
- (9) History of stroke in the past 3 years;

- (10) Severely impaired cognition (MoCA ≤10, FAST >5 or CDR >2);
- (11) Inability to have MRI and LP e.g. for MRI, metal implants or cardiac pacemaker or for LP, bleeding diathesis from disease states or from use of anticoagulants such as warfarin, heparin and related products, Rivaroxaban or Xarelto, Apixaban or Eliquis, Edoxaban or Savaysa, Dabigatran or Pradaxa. Subjects who can have either one LP or MRI will be enrolled;
- (12) Inability to have cognitive assessment due to hearing, vision, or language issues or due to severe impairment;
- (13) History of increased intracranial pressure (ICP);
- (14) In those who are unable to demonstrate that they understood the details of the study using the UBACC modified for EMERALD (i.e. lack of decisional-capacity to consent), a study partner/surrogate who can sign on their behalf will be required; otherwise, they will be excluded;
- (15) Use of phenobarbital or rifampin due to drug interaction.

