5.3. CONCOMITANT INTERVENTION

5.3.1. ALLOWED INTERVENTIONS

Participants will continue to receive their usual care from their regular primary care physicians. In the event that during the trial period, a participant is required to be on a LTRA (Montelukast or other similar agents), the prescribing physician and the subject will be informed they might be receiving Montelukast to avoid any overlap. If an alternative treatment is prescribed that is safe to be used with Montelukast, then they can continue on the study medications. Participants who start on a LTRA (or a drug that potentially lead to contraindication for using LTRA) clinically will have their study medication discontinued but will continue to be in the study and have their subsequent visits and measures completed.

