5.3.2. PROHIBITED INTERVENTIONS

Participation in another clinical trial or study is prohibited.

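### Exclusion 2 bars current leukotriene-antagonist users only if they also have asthma or exercise-induced bronchospasm, and no other rule covers use that predates randomisation

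*Combined protocol and SAP*

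**What the plan says.** Section 4.2, exclusion 2, is one numbered item with two parts joined by *and*: the first is "Current diagnosis of bronchial asthma or exercise-induced bronchospasm" and the second is "currently on Montelukast or other leukotriene receptor antagonists (Zafirlukast, Pranlukast"). In the protocol the word joining the parts is in bold.

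The other items and sections that might bear on current LTRA use are these:

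- Exclusion 1 covers "Intolerance to Montelukast".
- Exclusion 5 ends with a discretionary clause on any "other active medical condition that in the judgment of the study physicians would affect the safety of the subject or scientific integrity of the study".
- Exclusion 15 covers "Use of phenobarbital or rifampin due to drug interaction".
- Section 5.3.2 has a single entry: "Participation in another clinical trial or study is prohibited".
- Section 5.3.1 says what happens if an LTRA becomes necessary during the trial. The prescriber and participant are told that the study drug may be Montelukast, so that the two are not taken together, and "Participants who start on a LTRA (or a drug that potentially lead to contraindication for using LTRA) clinically will have their study medication discontinued", with follow-up continuing.
- Sections 6.1 and 6.10.2 provide for a medication inventory and for recording non-study medication, but attach no eligibility rule to either.

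**The concern.** Exclusion 2 appears intended to keep people already on the study drug or its class out of the trial. As worded, it does so only for those with one of two diagnoses. Section 2 names those diagnoses only as examples of what Montelukast is used for. Section 2.2 cites a case series of 17 people with cognitive impairment who were taking it. The protocol therefore does not itself assume that every user in this population has asthma or bronchospasm.

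The primary objective is at stake. Section 1 makes safety, dose-response and target engagement primary. Section 6.7 measures LTE4 and CysLT1 receptor activity at baseline, 6 and 12 months. Section 9.3 compares change over the study between arms and plots dose against receptor activity. A participant who enters on an LTRA has no untreated baseline for any of these, and total exposure is not what the allocation says it is.

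**Working it through.** **1. Logic of exclusion 2.** There are two conditions, a diagnosis (asthma or exercise-induced bronchospasm) and current LTRA use.

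| Diagnosis | On LTRA | As written (both needed) | Drug use alone excludes | Either excludes |
|---|---|---|---|---|
| no | no | eligible | eligible | eligible |
| no | yes | **eligible** | excluded | excluded |
| yes | no | eligible | eligible | excluded |
| yes | yes | excluded | excluded | excluded |

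The second row is the gap. The same list favours the literal reading: exclusions 4 and 10 join alternatives with *or*, and exclusion 11 uses *and* for MRI and LP, then says that being able to have one of them is enough to enrol.

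**2. Does another rule close the second row?** Exclusion 1 concerns intolerance, not tolerated use. Exclusion 5 concerns a medical condition, not a concomitant drug. Exclusion 15 names two other drugs. Section 5.3.2 concerns other studies. Section 5.3.1 is triggered by a need arising, or a drug started, after entry. No washout is stated. The row stays open.

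**3. Consequence by outcome.** The plan states no figure to reproduce here. Inputs: 1:1 allocation (Section 5.1), 15 per group and 36 enrolled (Section 3), analysis of change by mixed models (Section 9.3). Let *d* be the true difference in change between arms and *k* the number of background users in one arm. Assume that background use gives the full drug effect, which makes each result an upper bound.

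- *Outcomes that progress over the year, such as cognition.* A placebo-arm user changes as a treated participant does. The contrast becomes *d* × (1 − *k*/15).
  - *k* = 1: 1/15 = 6.7% lost
  - *k* = 2: 2/15 = 13.3% lost
  - *k* = 3: 3/15 = 20% lost
  - With all 36 analysed, 18 per arm: 1/18 = 5.6%, 2/18 = 11.1%, 3/18 = 16.7%
- *Receptor activity (LTE4), placebo arm.* A stable background user is already blocked at baseline and remains so, so the change is near zero, as for other placebo participants. The contrast in change is not diluted.
- *Receptor activity (LTE4), Montelukast arm.* A user already fully blocked at baseline has no room to change and contributes about 0 in place of *d*. The arm mean becomes *d* × (1 − *k*/15), again up to 6.7% lost per user.
- *Dose-response plot.* A placebo-arm user sits at dose zero with non-zero exposure. A Montelukast-arm user taking their own Montelukast has the study dose plus that supply. Points are misplaced along the dose axis, with no fixed direction of bias.
- *Safety.* Extra exposure in the Montelukast arm could widen the contrast, and active drug in the placebo arm could narrow it. The net direction is not determined.

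**4. Frequency.** The documents give none, so *k* = 0 to 3 is an assumed range. Under 1:1 allocation, 1 to 3 users on placebo corresponds to roughly 2 to 6 users in the whole trial of 30 to 36.

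**The case against.** A reader might infer that the plan accepts at entry the very exposure it forbids later, and so contradicts itself outright. The documents do not support that. Nowhere do they endorse background LTRA use; they do not address it. Section 5.3.1 concerns people who start an LTRA, and its evident aim is to prevent double exposure. Screening under Section 6.10.1 gathers medical information to judge safety and eligibility, and bottles are inspected for the medication inventory, so such use would probably be noticed. What stands is that noticing is not a rule: staff applying the listed criteria as written would have no stated ground for exclusion.

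A reader might also infer that each user pulls every treatment contrast towards no effect by 1/15. That does not follow either. The analysis is of change, so a stable user on placebo does not dilute the LTE4 contrast. Where 1/15 does apply, it needs background use to match the full effect of the escalated study drug. For safety and dose-response the direction can go either way.

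Finally, *and* might have been meant to list two separate exclusions. On that reading there is no loophole, but everyone with either diagnosis is also excluded, and the item still needs rewording because a single numbered item with a bolded conjunction does not say so.

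**Conclusion.** The point holds as a gap in the entry rule. Taken literally, exclusion 2 lets in a current LTRA user without asthma or exercise-induced bronchospasm, and neither the other exclusions nor Sections 5.3.1 and 5.3.2 deal with use that began before randomisation. This defeats the evident aim of Section 5.3.1.

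The size is small per person and unknown in total: at most about 6.7% of the contrast for each placebo-arm user on progressing outcomes, and a similar upper bound for each Montelukast-arm user on change in LTE4. Both figures assume 15 per arm and a full drug effect from background use. If no such person is enrolled, nothing is lost. The plan gives no power calculation against which to set a loss. The case for changing the text rests on the effect on primary-objective measures in a trial of 30 and on how little the change costs, not on a demonstrated bias.

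**What to change.** Reconcile Section 4.2, exclusion 2, with Section 5.3.1. Separate the diagnosis condition from the drug-use condition, so that the entry rule on current LTRA use does not depend on an asthma or bronchospasm diagnosis and agrees with the aim of avoiding double exposure.

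Two matters are for the sponsor to decide and state: whether the diagnosis on its own excludes, and how LTRA use stopped shortly before screening is handled, since a rule on current use alone leaves that open and baseline values might still be affected.

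The cost is a one-line protocol amendment and perhaps a few candidates lost at screening. The sample size and the study procedures do not change.

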Section of Geriatrics and Gerontology

Department of Medicine and Neurology

Emory University

[contact]

[name] MPH (Co-Investigator, Postdoc Fellow)

Department of Neurology

Emory University

[contact]

[name] (Co-investigator, Neuropsychologist)

Department of Neurology

Emory University

[contact]

[name] (Statistician)

Department of Neurology

Emory University

[contact]

PARTICIPATING STUDY SITES

Wesley Woods Health Center

Emory University Hospital Clinical Research Network

Executive Park Medical Campus

PRÉCIS

Study Title

Effects of Montelukast Therapy on Alzheimer's Disease

Acronym

EMERALD

Objectives

Our *primary objective* is to determine the safety, dose-response and target engagement of the treatment with escalating doses of Montelukast in those with mild cognitive impairment (MCI) or early Alzheimer's disease (AD) dementia.

Our *secondary objectives* are to assess the efficacy and estimate the effect size of up to 1-year treatment of Montelukast on biomarkers of neurodegeneration and cognition in MCI/early AD dementia.

Design and Outcomes

This is a double-blind placebo-controlled randomized clinical trial that compares Montelukast to placebo in individuals with MCI and early AD dementia. Our measures include cognitive function, CSF biomarkers and neuroimaging (cerebral perfusion and markers of vascular brain damage).

Interventions and Duration

The intervention includes Montelukast (10, 20, or 40 mg) or placebo. The duration of the study is 1 year.

Sample Size and Population

Our target population includes subjects who are 50 years or older with MCI and early AD dementia. Our sample size is 30 for this trial.

TABLE 1. SCHEDULE OF PROCEDURES FOR THE DURATION OF THE STUDY

Phase:	SCREEN	BASELINE	FOLLOW-UP			
Number of visits	1-2 [@]	1-2				
Months	-1	0	1.5	3	6	12
Informed Consent	X					
Cognitive screening	X					
Screening labs	X*					
CSF for biomarker and molecular analysis		X**				X [^]
Weight/Height	X	X	X	X	X	X
Blood Pressure	X	X	X	X	X	X
Safety labs			X [#]	X [#]	X [#]	X [#]
Brain MRI		X				X
Vascular function measures (PWV/PWA)		X				X
Cognitive Battery		X			X	X
Functional battery (FAQ, IADL, SPPB)		X***				X
LTE₄ testing		X			X	X
Blood for biospecimen banking		X			X	X
Time (in minutes)	60-120	150-210	30	30	120-150	120-150

^{*}: Screening labs include: CBC, CMP (BUN, Cr, electrolytes, liver function test (LFT)), B12, TSH and PT/INR.

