6.10. SCHEDULE OF EVALUATIONS

6.10.1. SCREENING

Individuals who express an interest will first participate in a screening process. During the remote (phone/virtual) or in-person screening visit, after informed consent has been obtained either on paper or electronically, we will collect demographic and medical information, and perform a series of tasks to determine subject safety and eligibility to participate in the study e.g. blood pressure checks, cognitive testing, lab testing. See Table 1 for detailed information on study procedures performed at screen visit.

Participants meeting eligibility criteria detailed in Section 4 (Selection and enrollment of participants) will be scheduled for the baseline visit.

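### Exclusion 6 prints the vitamin B12 cut-off as 250 ng/mL, above any plausible result, so as written it cannot identify low B12: a minor unit correction

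*Combined protocol and SAP*

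**What the plan says.** The sixth exclusion in section 4.2 covers factors other than the disease under study that may contribute to impaired cognition. It names two examples, each with a number in brackets. The examples read "uncontrolled hypothyroidism (TSH >10 mU/l) or untreated low vitamin B12 (<250 ng/mL".

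B12 is measured in the trial. The footnote to Table 1 reads "Screening labs include: CBC, CMP (BUN, Cr, electrolytes, liver function test (LFT)), B12, TSH and PT/INR", and gives no unit or reference range for B12.

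The result bears on entry. Section 6.10.1 states: "Participants meeting eligibility criteria detailed in Section 4 (Selection and enrollment of participants) will be scheduled for the baseline visit".

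The documents give no other B12 threshold, and no other unit, laboratory range or override for this item.

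**The concern.** The bracketed number is what turns the words about low B12 into a rule that can be applied to a laboratory result. A cut-off in ng/mL is 1,000 times the same number in pg/mL. If ordinary serum levels run in the hundreds of pg/mL, no ordinary result reaches the printed value. Every candidate is then low, and only those already treated for it escape the exclusion.

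What is at stake is an eligibility threshold in current protocol text that does not do its job. Taken at its word, it would screen out everyone not on B12 treatment. If staff instead read the number in another unit, the people they enroll still fail the criterion as printed, and nothing in the protocol explains the difference.

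**Working it through.** The plan derives no figure here, so there is nothing to reproduce. The check is a unit conversion followed by a comparison.

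**Inputs from the documents**
- Cut-off: below 250 ng/mL, for untreated candidates (section 4.2, item 6).
- B12 is a screening laboratory test (Table 1 footnote).
- Meeting the section 4 criteria is the condition for going on to baseline (section 6.10.1).

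**Input that is an assumption**
- Usual serum B12 of about 200 to 1,000 pg/mL. This is general laboratory knowledge and does not come from the documents, so a much wider range of 100 to 10,000 pg/mL was also tried.

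**Conversion** (1 ng = 1,000 pg)
- As printed: 250 ng/mL × 1,000 = 250,000 pg/mL.
- Same number read as pg/mL: 250 / 1,000 = 0.25 ng/mL.
- Ratio of the two cut-offs: 250,000 / 250 = 1,000.

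**Comparison.** The third column is 250,000 divided by the level in pg/mL.

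| Assumed B12 (pg/mL) | In ng/mL | Printed cut-off ÷ level | Below 250 ng/mL? | Below 250 pg/mL? |
|---|---|---|---|---|
| 100 | 0.1 | 2,500 | yes | yes |
| 200 | 0.2 | 1,250 | yes | yes |
| 500 | 0.5 | 500 | yes | no |
| 1,000 | 1.0 | 250 | yes | no |
| 10,000 | 10.0 | 25 | yes | no |

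With the printed unit, every row meets the exclusion. With the same number in pg/mL, the rule separates: 100 and 200 fall below it, and 500 and above do not. Because 1 pg/mL equals 1 ng/L, a slip of n for p, or of mL for L, would give the printed text, and both lead back to the same cut-off.

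**The case against.** The strongest reply is that nobody would apply the criterion literally. The item speaks of low B12 as one example of a contributing factor, and the word low has no function if every untreated person qualifies. Staff would probably read 250 in whatever unit the laboratory reports. A literal application would show itself at once, since nearly every untreated candidate would fail screening. All of this stands, and it is why the point is minor. It does not rescue the printed threshold: the bracket is the only numerical definition of low B12 in the protocol, just as the TSH value is for hypothyroidism.

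A second reply is that the replacement unit cannot be read from the documents. They state no laboratory unit, range or second threshold, so a molar unit or a mistyped number cannot be ruled out. This also stands, and it limits the remedy. A misread letter in the PDF text is a further possibility. The other units in the same list, such as those for creatinine and TSH, look ordinary, so nothing points to a misread, but the source file is easily checked.

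Two stronger readings are tempting and are not supported:
- **A sample made up only of B12 users.** A reader might infer this from the literal text. It would need staff to keep applying a rule that its own wording resists, and the documents give no sign of that.
- **A per-protocol set that cannot be verified.** Section 9.1 says that intention-to-treat and per-protocol analyses will be done. It does not define the per-protocol set or tie it to exclusion 6, so any difficulty in checking that set comes from the missing definition and not from the B12 unit.

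**Conclusion.** The point holds as a minor error in an operative eligibility threshold. The printed cut-off is 1,000 times the same number in pg/mL. It is 250 to 1,250 times the assumed usual levels of 200 to 1,000 pg/mL, and 25 to 2,500 times any level from 10,000 down to 100 pg/mL. As written it cannot tell low from normal B12.

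The conversion is exact. That no plausible result reaches the cut-off rests on the assumed serum range, but with a margin of 25-fold at the top of the wide range the conclusion does not depend on where that range is drawn.

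The likely practical effect is small. The planned enrollment of 36, the target of 30, the randomization strata and the mixed-model analysis do not use this number. Whether 250 is a suitable cut-off in any unit is a clinical matter on which nothing is said here.

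**What to change.** Correct the unit in section 4.2, item (6). The number as printed fits pg/mL, which is the same as ng/L. Before making the change, the sponsor should confirm both the intended value and the intended unit against the reporting unit of the screening laboratory, and should check the source file of the protocol. The same unit should appear on the screening form, so that the result is recorded and judged on one scale.

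The cost is a one-word protocol correction and, if needed, a matching edit to the form. No added testing is required, because B12 is already a screening test.

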4.3. STUDY RECRUITMENT

Potential participants will be identified through community activities, health fairs, advertisements in periodicals and local newspapers, and patient referrals. Below we describe our recruitment venues:

- (1) *The Emory Alzheimer's Disease Research Center (ADRC)* Clinical Core registry of research participants will be utilized for recruitment. Participants have agreed to be referred to other studies.
- (2) *Community-based recruitment:* Community education sessions in local neighborhoods e.g. churches or barbershops will be conducted, and attendees will be invited to participate in this study.
- (3) *MindMate App recruitment:* MindMate users have the opportunity to first express their interest in clinical studies within the 'Research' section of the app. MindMate can also reach out to users once they have consistently utilized the app, usually after 3-4 weeks, and ask the user if they would like to receive further information when a matching clinical study is available in their area. All users that are interested in participating in a clinical study must then go through a multi-stage opt-in & consent process that will be conducted in-person or electronically. After MindMate matches a user to an open clinical trial, they automatically ask if they're happy to be contacted by a researcher to learn more about an open study they might qualify for.
- (4) *Physician recruitment:* Local physicians (primary care or specialty physicians) will be informed of the study and its criteria and provided information about referral to the study personnel. In addition, flyers for the study will be posted at outpatient areas in the local medical facilities.

